### 13.1.3 Analysis Sets

#### *Safety Set*

The Safety Set will consist of all subjects who are randomized and receive study drug. Subjects in this analysis set will be used for demographic, baseline characteristics and safety summaries.

#### *Pharmacokinetic Set*

The PK Set will consist of all subjects who receive study drug and have at least 1 measurable plasma concentration of CVN058.

#### *Pharmacodynamic Set*

The PD Set will consist of all subjects who receive study drug and have at least 1 post-dose PD measurement.

If any subjects are found to be noncompliant in dosing schedule or with incomplete data, a decision will be made on a case-by-case basis as to their inclusion in the PK and PD endpoint analyses, but data for all subjects will be presented in the subject listings.

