## **8.5 Unblinding Procedure**

The investigational drug blind shall not be broken by the investigator unless information concerning the investigational drug is necessary for the medical treatment of the subject. All study assessments and assignment of causality for AEs should be performed, if possible, prior to unblinding. In the event of a medical emergency, if possible, the medical monitor should be contacted before the investigational drug blind is broken to discuss the need for unblinding.

For unblinding a subject, the investigational drug blind can be obtained by contacting the dispensing pharmacist.

The sponsor must be notified as soon as possible if the investigational drug blind is broken. The date, time, and reason the blind is broken must be recorded in the source documents and the same information (except the time) must be recorded on the eCRF.

If any site personnel are unblinded, investigational drug must be stopped immediately and the subject must be withdrawn from the study.

Having completed a blinded interim analysis of data for the first 12 completed subjects, the Sponsor has determined that those data will be unblinded per a change to the study plan introduced in Protocol Amendment 4. All data from subsequently enrolled subjects will remain blinded until the study is concluded.

No change should be made to any prior assessments or data of any subject after unblinding of his/her treatment assignment.

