## 13.0 STATISTICAL METHODS

### 13.1 Statistical and Analytical Plans

A statistical analysis plan (SAP) will be prepared to describe and direct study data analyses. The SAP will provide details regarding the definition of analysis variables and analysis methodology to address all study objectives, and will be finalized prior to data analysis.

A targeted data review will be conducted prior to database lock. This review will assess the accuracy and completeness of the study database, subject evaluability, and appropriateness of the planned statistical methods.

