#### 13.1.2 Unblinded Interim Analysis

During the study, upon review of the outputs from the blinded interim analysis (which included data only from the first 12 subjects, who had already completed the study), the Sponsor determined that an unblinded analysis of those interim data is necessary to properly inform decisions about study continuation and dose selection. Unblinding of the interim analysis data is thus introduced in Protocol Amendment 4, and the SAP will be modified accordingly and finalized prior to the unblinded interim analysis.

An analysis unblinded to treatment and structured identically to the Primary Analysis will be performed using data only from the first 12 subjects, who have already completed the study. The analysis will consist of a comparison of the post dose PD parameter Mean Amplitude of Duration MMN versus the same parameter at time-matched placebo period timepoints. This analysis will utilize the O'Brien-Fleming group-sequential stopping boundary to control alpha.

SAS Proc SEQTEST will be employed to perform the conditional power analysis. Study stoppage for futility may occur if conditional power is very low.

Additionally, prior to study stoppage, the unblinded interim data will be used to calculate the conditional power values associated with protocol-permissible increases in the sample size (i.e., up to N=40), based on the observed unblinded data at the time of the interim analysis.

CONFIDENTIAL

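### The case-by-case inclusion rule and the pre-lock review were not adapted to the unblinded interim, so PD Set membership of the first 12 subjects can be decided with their treatment and MMN results known

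*Protocol*

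**What the plan says.** Section 13.1.3 of the protocol defines the Pharmacodynamic (PD) Set as dosed subjects with one or more post-dose PD measurements. It then makes an exception with two triggers: "If any subjects are found to be noncompliant in dosing schedule or with incomplete data". For such subjects the protocol settles nothing in advance and says only that "a decision will be made on a case-by-case basis as to their inclusion in the PK and PD endpoint analyses". All subjects still appear in the listings. The two triggers are not defined, and the text does not say who decides, when, or with what knowledge of treatment.

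Section 13.1 adds a second point of decision: "A targeted data review will be conducted prior to database lock". The remit of that step is wide, in that, as the section puts it, "This review will assess the accuracy and completeness of the study database, subject evaluability, and appropriateness of the planned statistical methods". It is not described as blinded.

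Section 8.5 then states: "Having completed a blinded interim analysis of data for the first 12 completed subjects, the Sponsor has determined that those data will be unblinded". Section 13.1.2 describes the use: "An analysis unblinded to treatment and structured identically to the Primary Analysis will be performed using data only from the first 12 subjects". The parameter is duration MMN amplitude, which is the primary endpoint, and the reason given is that "an unblinded analysis of those interim data is necessary to properly inform decisions about study continuation and dose selection". Section 11 provides for no steering, safety-monitoring or endpoint committee.

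Three provisions work the other way. Section 8.5 keeps later subjects blinded to the end of the study. It also bars alteration of a subject's earlier data or assessments once the assignment is known. Section 13.1.2 requires the SAP to be revised and made final before the unblinded interim is run.

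**The concern.** A discretionary inclusion rule does little harm while nobody who applies it knows treatment or outcome. Here the sponsor will hold both for the first 12 subjects while the trial goes on, and the protocol puts no wall between those who see the interim comparison and those who judge evaluability. With about 20 subjects, one exclusion chosen with its result in view can move the primary comparison. The difficulty is an interaction between two parts of the protocol: the inclusion and review rules suit a blinded trial, and the unblinding was added without changing them.

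**Working it through.** **1. Do the safeguards fix who is analysed among the 12?**

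| Provision | What it secures | Fixes membership of the 12? |
|---|---|---|
| 8.5, no alteration after unblinding | Recorded data and assessments | No; leaving a subject out of an analysis alters neither |
| 8.5, later subjects stay blinded | Decisions from subject 13 on | No; does not reach the 12 |
| 13.1.2, SAP final before the interim | Method, and exclusion rules if the SAP holds any | Not by the protocol's text, which keeps inclusion discretionary |
| 13.1, review before lock | Order relative to lock | No; lock falls after the interim |
| 13.1.3, listings of all subjects | Transparency | No; allows re-analysis only |

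The inclusion and review wording also stands in the two earlier protocol versions in the same file. There the only interim look, where there was one, was blinded.

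**2. Share of the data.** Planned completers are 20 (section 13.2): 12/20 = 60%. The ceiling is 40 (section 13.1.2): 12/40 = 30%.

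**3. The plan's own power figure, to settle which error rate to use.** Section 13.2 claims about 80% power for n = 20, d = 0.5, alpha = 0.10, with sidedness not given. For a paired t-test the noncentrality is d√n = 0.5 × √20 = 2.236.

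- One-sided 0.10: normal check 2.236 − 1.282 = 0.954, Φ = 83.0%; noncentral t gives 81.7%.
- Two-sided 0.10: normal check 2.236 − 1.645 = 0.591, Φ = 72.3%; noncentral t gives 69.5%.

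The claim reproduces only one-sided. The check below therefore uses one-sided 0.10, and one-sided 0.025 as one side of the 95% interval in section 13.1.6.

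**4. Effect of an outcome-aware exclusion.** The documents give no figures for this, so the following is assumed: no drug effect; 20 independent paired differences (one dose against placebo, signed so that larger is better) from N(0,1); one t-test, t = mean/(SD/√n) on n − 1 degrees of freedom; interim alpha spending ignored. Of the 12 unblinded subjects, m have an arguable deviation unrelated to outcome. The least favourable of these m is dropped and the remaining 19 are tested. One million simulated trials give these rejection rates:

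| Exclusion | Nominal 0.10 | Nominal 0.025 |
|---|---|---|
| None | 0.100 | 0.025 |
| Worst of m = 2 | 0.123 | 0.032 |
| Worst of m = 3 | 0.138 | 0.038 |
| Worst of m = 4 | 0.149 | 0.042 |
| Worst one of all 12 | 0.195 | 0.063 |
| Worst two of all 12 | 0.288 | 0.109 |

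The last two rows treat all 12 subjects as eligible for exclusion, which the rule in section 13.1.3 does not allow. They are a ceiling only.

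**The case against.** The best reply is that the gap is small and mostly closed. Evaluability rules are ordinary SAP content, and the SAP is to be final before the interim. Data and earlier assessments may not be altered after unblinding. The inclusion rule has only two triggers, and both are uncommon among these 12: the blinded interim was to be triggered by MMN data from all three periods (section 13.1.1), the subjects have completed the study, and each dose is a single administration under observation (section 9.2). What remains is mainly timing, such as the 7 to 10 day washout. The interim also uses the structure of the primary analysis, so membership of the 12 has to be settled in practice to run it, and a later removal would be visible.

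Most of this stands, and it limits the size of the point. It does not remove it: the protocol itself states a discretionary rule and a review of methods, and nothing in it ties the final analysis to the membership used at the interim.

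A reader might infer more than the text supports:

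- *That exclusions are planned for after unblinding.* Section 13.1.3 gives no date. The later timing is only allowed, through the pre-lock review.
- *That a subject may be dropped for a poor MMN value, so that error rises to 0.19 to 0.29.* No rule permits this.
- *That the review may change the method.* Section 13.1 says that it assesses appropriateness. It neither authorises nor forbids a change.
- *That the damage could not be undone.* All subjects are listed, so an all-subject re-analysis remains possible.

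**Conclusion.** The point holds in a limited form. For 12 of the 20 planned subjects, the protocol leaves room for inclusion decisions made with treatment and primary outcome known, and no provision in it fixes their analysis-set membership beforehand. This is an opportunity for bias, with no evidence that anyone has used it or intends to.

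A plausible size is an increase from 0.10 to about 0.12 to 0.15, or from 0.025 to about 0.03 to 0.04. That rests on the assumed count of two to four arguable deviations, on normal paired differences, and on a single comparison in place of the three-treatment crossover model with an O'Brien-Fleming boundary. The 60% share presumes that N stays at 20 and that the dose compared is kept after the interim. The amendment is worth making because it is nearly free and, under the same model, holds the final test at its nominal level.

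**What to change.** Amend sections 13.1, 13.1.2 and 13.1.3 as follows:

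- Before the first 12 subjects are unblinded, record and sign off their PD Set membership and the evaluability of each session. Use the same membership at the final analysis.
- Make the primary MMN analysis include every recorded post-dose session, in line with the PD Set definition. Show exclusions only as a sensitivity analysis.
- State that the section 13.1 review of later subjects is done blinded, and that it may not move the primary method away from the SAP version finalized before the unblinded interim.

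Sections 8.5 and 13.1.2 speak of the unblinding as still ahead, so the sign-off is feasible. If it has already taken place, the second and third changes still protect the primary result.

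The cost is one sign-off on 12 subjects and some wording. The sponsor gives up later flexibility, and a few deviating sessions stay in the primary analysis. Sample size and planned power do not change.

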### 13.1.4 Analysis of Demographics and Other Baseline Characteristics

Demographic and baseline characteristics will be summarized by sequence and overall. Summary statistics (number of subjects, mean, median, standard deviation, minimum and maximum) will be generated for continuous variables (e.g., age and weight) and the number and percentage of subjects within each category will be presented for categorical variables (e.g., gender, ethnicity, race, smoking status, and caffeine consumption).

### 13.1.5 Pharmacokinetic Analysis

The concentration of CVN058, and its metabolite if appropriate, in plasma will be summarized over each scheduled sampling interval using descriptive statistics (arithmetic mean, SD, median, minimum and maximum). Individual plasma concentration data versus time will be presented in a data listing.

Descriptive statistics will be used to summarize the plasma PK parameters for CVN058, and its metabolite if appropriate. In addition, geometric mean and percent coefficient of variation will be computed for  $C_{max}$  and  $AUC_t$ .

A more detailed analysis will be presented in the SAP.

### 13.1.6 Pharmacodynamic Analysis

Observed values for the PD parameters (MMN and exploratory PD parameters) will be summarized by treatment and compared to placebo using summary statistics. Comparison of post-dose PD parameters from a time-matched placebo period timepoint will be analyzed using analysis of covariance (ANCOVA) with factors for sequence, subject nested within sequence, period, and treatment. Two-sided 95% confidence intervals will be constructed for the LS mean of observed differences in PD parameters, comparing CVN058 and placebo at a time-matched post-dose time point.

Effect size will be calculated for comparisons of CVN058 to placebo using Cohen's *d* which expresses the difference between the means of 2 groups as a function of their pooled standard deviation.

Exposure-response relationships for CVN058 will be explored graphically.

### 13.1.7 Safety Analysis

The Safety Set will be used for all summaries of TEAEs, laboratory tests, and vital signs. An increase in weight by 7% should be indicated as Clinically Significant or Not Clinically Significant and assessed on a case by case basis. All safety data will be summarized by treatment.

AEs will be presented in listings. TEAEs will be classified according to system organ class and preferred term and will be tabulated with a breakdown by treatment and by event severity. Similar TEAE tabulations will be performed on those events assessed by the investigator as related to study drug.

Individual results of vital signs will be listed and observed values and changes from Baseline in vital signs will be summarized by treatment.

Physical exam findings, suicidality assessments (C-SSRS), and PANSS scores will be presented in data listings.

Baseline values will be the latest observation prior to dosing in the first study period. Thus, for most assessments, the Baseline value will be the Day 1 pre-dose observation; for Clinical Laboratory assessments, the Baseline values will be from the Screening Visit (Day -28).

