#### 5.2.2 Secondary Endpoint

- Percentage of subjects who experience at least 1 TEAE
- Percentage of subjects who experience at least 1 clinically significant abnormal laboratory test result

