### **9.3.3 Final Visit/End of Treatment**

The Final Visit additional assessments will occur prior to Discharge from the clinic at the end of Treatment Period 3, Day 1, as outlined in [Appendix A](#).

For all subjects who received any study medication, the investigator must complete the End of Study eCRF page.

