**Table 9.c Approximate Blood Volume**

Sample Type	Sample Volume (mL)	Screening (x1)	Number of Samples per Period (x 3 Periods)	End of Treatment	Total Volume (mL)
Safety Laboratory Samples (a)	12.5	1	--	1	25
Hepatitis Panel	5	1	--		5
FSH (b)	3	1	--		3
PK Samples	6	--	9	--	54
DNA Sample	6	--	1 (c)	--	6
RNA Samples	5	--	6	--	30
Total Blood Sampling Volume (per Study)					123

(a) Includes Hematology, serum chemistry, and coagulation panel.

(b) FSH level will be obtained for female subjects at Screening if they are postmenopausal (i.e. last regular menstrual cycle >2 years) and not surgically sterile.

(c) Only collected in Day 1, Period 1.

The maximum volume of blood at any single day is approximately 40 mL, and the approximate total volume of blood for the study is approximately 123 mL.

Direct venipuncture is the preferred method of blood collection. Any other method will need to be approved by the Sponsor.

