## Appendix A Schedule of Study Procedures

Study Day:	Visit 1: Screening	CVN058 and Placebo Treatment Periods 1, 2, and 3 (a)			End of Treatment	Early Termination (c)	Follow-up  Day 7-10 After End of Treatment (b)
		Day 1 pre-dose	Day 1 post-dose	Period 3, End Day 1			
Informed consent	X						
Inclusion/exclusion criteria	X	X					
Demographics	X						
Reproductive Status	X						
Social History	X						
Medication history	X						
Physical examination	X	X			X	X	
Vital signs (d)	X	X	X			X	
Weight, height, and BMI (e)	X				X	X	
Concomitant medications (f)	X	X	X			X	X
Medical history (g)	X						
Clinical laboratory tests (h)	X				X	X	
Hepatitis panel	X						
Audiometric Screening and Tone Matching test (i)	X						
FSH (j)	X						
Pregnancy test (hCG), serum except as noted	X	X (urine)				X	
Urine drug and saliva alcohol screen	X						
ECG (k)	X						
EEG battery (l)			X				
MMN (m)				X			
DNA sample collection (n)		X					
RNA sample collection (o)		X	X				
PK blood collection (p)		X	X			X	
Study drug dosing (q)			X				
PTE assessment (r)	X	X					
AE assessment (s)			X			X	X
C-SSRS (t)	X		X			X	
PANSS (u)	X		X			X	

Footnotes are on last table page.

CONFIDENTIAL

(a) Minimum 7-day and maximum 10-day washout period is required in between Treatment Periods 1, 2 and 3.

(b) The Follow-up Visit will occur by telephone 7-10 days after End of Treatment unless abnormal, clinically significant findings were observed upon discharge. In these cases, subjects must then be brought back to the clinic for re-evaluation per investigator's discretion.

(c) Conduct procedures for subjects discontinued early per Protocol [Section 7.6](#). The PK sample should be collected at the Early Termination Visit, if within 1 hour of a scheduled PK time point.

(d) Vital signs (oral temperature, respiration, pulse, and blood pressure) will be obtained at Screening, and in Periods 1, 2, and 3 (pre dose [within 30 minutes prior to dosing], and at 1 and 5 hours post dose), and at Early Termination (if applicable), and if clinically indicated according to Investigator discretion at the Follow-up visit. Vital signs will be collected with a window of  $\pm 15$  minutes.

(e) Height and BMI will be collected at Screening only.

(f) Record all patient medications from Screening and throughout the study.

(g) All new medical history arising after signing ICF should be recorded as PTE or AE.

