(h) Clinical laboratory tests (hematology, serum chemistry, urinalysis, and coagulation) will be collected at Screening and prior to check-out at End of Treatment or Early Termination, and at the Investigator discretion if a Follow-up Visit is indicated.

(i) Audiometric Screening assessment conducted according to local practice.

(j) A FSH level will be obtained on post-menopausal women (defined as continuous amenorrhea of at least 2 years and not surgically sterile).

(k) ECGs will be collected with a window of  $\pm 2$  minutes.

(l) For the EEG battery, testing will be done at Day 1 starting approximately 1.5 hours post dose for each period and will last approximately 3 hours. NOTE: Subjects should refrain from drinking coffee and smoking approximately 1 hour prior to the EEG assessment until discharge from clinic at the end of the afternoon.

(m) MMN will be the first EEG assessment conducted in the battery. EEG (MMN) assessment will be collected with a window of  $\pm 60$  minutes.

(n) One blood sample (6 mL) will be collected for pharmacogenomic analysis prior to study drug administration on Day 1 of Period 1 only. If isolation of DNA from the first sample was not successful or possible, a second aliquot of blood may be taken, if feasible.

(o) Two 2.5 mL whole blood samples will be collected for each Period (Periods 1, 2, and 3) on Day 1 at pre-dose, and 5 hours post- dose.

(p) Blood samples (6 mL) for PK analyses will be collected at pre -dose (within 15 minutes prior to dosing), and 1 and 5 hours post dose. PK collection for pre-dose will be (within 15 minutes prior to dosing),  $\pm 15$  minutes at the 1 hour post-dose time point, and  $\pm 30$  minutes at the 5 hour post-dose time point.

(q) Dosing will only occur on Day 1 of each period, and signals the start of the post-dose Day 1 visit assessments.

(r) PTEs will be collected from signing of informed consent up until dosing on Day 1; PTEs will be captured on the AE CRF page.

(s) Any adverse event with onset or exacerbation after dosing on Day 1 of Period 1 will be captured as an AE or SAE.

(t) The Screening/Baseline C-SSRS will be administered at Screening and the Since Last Visit C-SSRS will be administered after EEG/ERP collection on each dosing day, and End of Treatment or Early Termination (if applicable).

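### Section 13.1.7 asks for laboratory results by treatment, but a completer's only scheduled post-dose sample comes after all three regimens

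*Protocol*

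**What the plan says.** The file holds more than one version of the protocol. All references here are to the latest, the one that contains Section 13.1.7.

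- **Section 13.1.7, scope and rule.** "The Safety Set will be used for all summaries of TEAEs, laboratory tests, and vital signs". The same paragraph then rules: "All safety data will be summarized by treatment". Laboratory tests are not exempted.
- **Section 13.1.7, baseline.** "Baseline values will be the latest observation prior to dosing in the first study period". For laboratory tests the baseline is the Screening value. Vital-sign changes from this baseline are to be tabulated by treatment.
- **Section 5.2.2.** One of the two secondary endpoints is "Percentage of subjects who experience at least 1 clinically significant abnormal laboratory test result".
- **Appendix A, footnote (h).** Laboratory tests "will be collected at Screening and prior to check-out at End of Treatment or Early Termination".
- **Section 9.3.3.** The End of Treatment assessments take place "prior to Discharge from the clinic at the end of Treatment Period 3, Day 1".
- **Table 9.c.** Safety laboratory samples: one at Screening, one at End of Treatment, and a dash in the column for the treatment periods.
- **Section 9.1.8.** The investigator may order further tests, but they are entered in the database only if judged clinically significant.
- **Appendix A, footnote (d).** Vital signs, by contrast, are taken "in Periods 1, 2, and 3 (pre dose [within 30 minutes prior to dosing], and at 1 and 5 hours post dose".

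**The concern.** A by-treatment table in a crossover needs at least one observation that belongs to each treatment. Vital signs have that: every period has its own pre-dose and post-dose readings. Laboratory tests do not. A completer has a Screening sample and one sample at the end of the last dosing day, by which time all three regimens have been given.

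Following Section 13.1.7 literally would mean attaching that one sample to a treatment. The obvious label is the last regimen received. Differences between columns would then reflect which subjects happened to finish on which regimen. An abnormality caused by an active dose 7 to 20 days earlier could appear under placebo. The secondary laboratory endpoint would inherit the problem. So would laboratory-based adverse events: Section 9.1.8 has clinically significant abnormalities recorded as adverse events, and Section 10.1.8 dates an event from when its first signs were noted. An abnormality first seen at the final draw would therefore tend to be dated to Period 3.

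**Working it through.** **1. Number of scheduled laboratory draws.** Table 9.c gives 12.5 mL per safety sample and 25 mL per subject: 25 / 12.5 = 2 draws, one at Screening and one at End of Treatment. The table's total reproduces: 25 + 5 + 3 + 54 + 6 + 30 = 123 mL. So there is no hidden laboratory draw in Periods 1 or 2, in agreement with footnote (h).

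**2. What precedes the post-dose draw.** Periods are separated by a 7 to 10 day washout. At the Period 3 draw, the Period 2 dose lies about 7 to 10 days back and the Period 1 dose about 14 to 20 days back (twice 7 to twice 10). The Period 3 dose was given the same day.

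**3. Columns if the sample is labelled by the last regimen.** Period 3 in Table 6.a, sequences 1 to 6, reads C, C, B, B, A, A. Each regimen is last in 2 of 6 sequences.

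- 20 completers: 20 × 2/6 = 6.7 per column, so about 6 or 7.
- 40 completers, the permitted maximum: 40 × 2/6 = 13.3 per column.
- The placebo column consists of sequences 5 (B, C, A) and 6 (C, B, A). Every completer in it has already had both active doses.

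**4. What the split does to the information.** With no events among n subjects, the one-sided 95% upper bound on the rate is 1 − 0.05^(1/n).

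| Completers | Per column | All subjects |
|---|---|---|
| 20 | n=6: 39%; n=7: 35% | n=20: 14% |
| 40 | n=13: 21%; n=14: 19% | n=40: 7% |

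The by-treatment table would therefore be both misattributed and much less informative than the overall one.

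**5. Vital signs, mean change by treatment.** In Periods 2 and 3 the stated baseline is about 7 to 10 and 14 to 20 days old, although a same-day pre-dose value exists. Assume, for illustration only, no drug effect and a drift of 0, +3 and +6 units over the three periods. With balanced sequences each treatment sits equally in each period, so every column, placebo included, shows a mean change of (0 + 3 + 6)/3 = +3. The same-period baseline gives 0. The difference between columns is 0 either way.

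**6. Vital signs, precision of the comparison with placebo.** Take equal variances (unit variance), within-day correlation ρw and one between-day correlation ρb. With the common baseline, the baseline cancels from a within-subject treatment contrast, whose variance is 2(1 − ρb). With same-period baselines the variance is 4(1 − ρw). The protocol gives no correlations; the values below are assumptions.

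| ρw | ρb | Common baseline | Same-period baseline |
|---|---|---|---|
| 0.7 | 0.5 | 1.0 | 1.2 |
| 0.7 | 0.6 | 0.8 | 1.2 |
| 0.8 | 0.5 | 1.0 | 0.8 |
| 0.8 | 0.6 | 0.8 | 0.8 |

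The same-period baseline is worse in two cases, equal in one and better in one.

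**The case against.** **No attribution rule is stated.** The protocol never says the final sample is credited to the last regimen, and a reader should not infer that it does. The detailed paragraphs of Section 13.1.7 prescribe by-treatment tables for adverse events and vital signs; laboratory tests are reached only through the general sentence. Section 5.2.2 does not word the laboratory endpoint as a comparison with placebo, and Section 13.1 leaves analysis details to the SAP. All of this is fair, and it is why the remedy is only a clarification. It does not rescue the sentence: laboratory tests are named just before it, and no attribution of a single sample taken after all three regimens would be sound.

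**The washout is long.** Section 4.3 gives mean half-lives of about 2.8 to 10.5 hours, so earlier doses will have cleared. But clearance of drug is not recovery of a laboratory value. Section 7.5 itself provides for enzyme elevations that persist beyond 2 weeks. The draw also falls on the last dosing day, so a change that takes more than hours to appear is more likely to belong to an earlier regimen.

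**Other samples exist.** Early Termination and discretionary tests are possible, and an early terminator may not have had every regimen. This stands as a limit on the statement, which concerns completers. These samples are selective and give no per-treatment denominator.

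**Safety tables in general.** A reader might infer that every by-treatment safety table fails. The documents do not support that. Dosing and adverse event onset can be placed in a period, and vital signs are observed after each dose, so those tables are sound, apart from laboratory-based events first detected at the final draw.

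**Vital-sign baseline.** A reader might also infer that the Period 1 baseline biases or weakens the comparison with placebo. In completers it cancels from the within-subject contrast, and the second table above shows no consistent loss. Individual vital signs and observed values are reported as well, so later pre-dose readings are not discarded altogether.

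**Conclusion.** The point holds for laboratory data. The by-treatment rule in Section 13.1.7 and the laboratory schedule cannot both be followed in a meaningful way: a completer's one scheduled post-dose sample follows all three regimens. If it were labelled by the last regimen, columns would hold about 6 or 7 of 20 completers, and every completer's placebo value would follow both active doses. The draw count comes from the protocol's own schedule and blood-volume table. The column sizes assume near-equal allocation to the six sequences, no dropout and unchanged dosages; replacing a dosage after the interim analysis could thin the columns further.

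The reach is limited. One secondary endpoint, the laboratory summaries and any laboratory-based adverse events first found at the final draw are affected. The MMN analysis, other adverse event tables and observed vital signs are not.

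For vital-sign change the matter is one of interpretation only. A change from the Period 1 value mixes response to that dose with drift over 7 to 20 days. The +3 illustration rests on an assumed drift, and no gain in precision against placebo is claimed.

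**What to change.** In Section 13.1.7, qualify the by-treatment sentence so that it does not cover scheduled laboratory tests or the laboratory secondary endpoint. State that these are summarised overall, from Screening to End of Treatment or Early Termination, with a breakdown by sequence if wanted. Add that adverse events based on a laboratory abnormality first detected at the final draw are flagged in the by-treatment table as not attributable to a single regimen.

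Optional: for the table of vital-sign changes, define baseline as the pre-dose value of the same period and keep the table of observed values as it is. Screening stays the baseline for laboratory tests.

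The cost is wording in the protocol and the matching lines in the SAP. No new data are needed, and the only loss is a by-treatment laboratory table that could not have been interpreted. Such a table would need samples the schedule does not take and that the first 12 subjects, who have already completed, can no longer provide; this point does not ask for them.
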